11.6.3 Clinical Laboratory

No laboratory safety data are collected and therefore will not be presented for this study.

11.6.4 Electrocardiograms

No ECG data are collected and therefore will not be presented for this study.

11.6.5 Vital Signs

Vital signs, length (cm) and weight (kg) will be assessed and recorded at all clinic visits (Days 1, 28, 56, and 90). Vital sign measurements will include pulse rate (bpm), pulse oximetry (SpO2), and body temperature (°C). Measurements are to be repeated if clinically significant changes are observed or a machine error occurs. Body temperature should be taken per standard of care at the site. Length will be measured twice and both values will be recorded. The average value of the 2 recorded lengths will be used for any analysis.

A summary table with descriptive statistics for actual and CFB values, will be presented by visit and treatment group. PCI criteria for pulse rate, pulse oximetry (SpO2), and body temperature are given inTable 5.

Confidential Page 39 of 50

Table 5. Vital Signs PCI

Vital Signs Parameter	PCI Criteria
Body temperature	If temperature location is Axillary: < 36.5°C or > 37.5°C
	If temperature location is Ear: < 35.8°C or > 38.0°C
	If temperature location is Forehead: < 36.4°C or > 38.0°C
	If temperature location is Rectal: < 36.6°C or > 38.0°C
Pulse Rate	< 85 bpm or > 190 bpm
SpO2	< 95%

Temperature values should be rounded off to 1 decimal before applying PCI.

The number and percentage of participants meeting PCI for each vital sign (temperature, pulse rate, and pulse oximetry) at Day 28 visit and for any post-baseline visit will be summarized by treatment group in a table.

A participant listing of vital signs will be presented with actual values and a flag for values meeting PCI criteria.

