the control group [Frese 2017]. The dominance of *B. infantis* influenced beta diversity (diversity between samples). However, there were no differences in terms of microbial species richness (alpha diversity) as the Shannon diversity index was similar between control and *B. infantis* groups. Lack of differences in alpha diversity between control and *B. infantis* is consistent with previous reports on breast-fed infants. Brink, et al, reported lower alpha diversity in infants receiving human milk compared to infant formula [Brink 2020].

Of note, the quality control of the study intervention will be important since contamination is a potential known risk for this type of product.

Bacterial transmigration and bacteremia have been described in case reports of *B. infantis* products but are considered coincidental, and not pathogenic. No bacterial transmigration or bacteremia cases have been reported with Bi-26 in ongoing infant clinical trials.

Potential benefits of supplementing infant feeding in low-income countries with *B. infantis* include a possible reduction in gut inflammation, and improved nutrient adsorption, potentially resulting in improved health outcomes. The findings from the SYNERGIE study with *B. infantis* strain EVC001 support the potential for positive clinical outcomes with *B. infantis* supplementation [Barratt 2022]. In the SYNERGIE study, following hospital discharge and acute phase management, infants were transferred to nutritional rehabilitation units and randomized to receive either 8 billion CFUs (target) of *B. infantis* EVC001 (n=20), 8 billion CFUs (target) or EVC001 plus probiotic LNnT (n=21), or lactose placebo (n=21). Infants received 4 weeks of supplementation and were followed for an additional 4 weeks for outcomes. Researchers observed that daily supplementation with *B. infantis* for 4 weeks was associated with *B. infantis* colonization and an increase in anthropometric measures, including WAZ [Barratt 2022]. This study provides support for a larger study assessing weight gain in underweight infants following supplementation with other *B. infantis* strains.

3. Objectives and Endpoints

See Table 1.

4. Study Design

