11.6.7 Bilateral Pedal Edema

The number and percentage of participants with bilateral pedal edema will be presented by treatment group for baseline and any post-baseline visit.

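### The vital-signs PCI table pools low and high values for temperature and pulse rate and shows no baseline status, which dilutes a one-directional excess such as fever in relative terms (minor)

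*SAP*

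**What the plan says.** SAP 11.6.5, Table 5, gives the criteria for potentially clinically important (PCI) vital signs. Temperature has a two-sided criterion for each measurement site, for example "If temperature location is Axillary: < 36.5°C or > 37.5°C". Pulse rate is also two-sided: "< 85 bpm or > 190 bpm". SpO2 has a lower limit only.

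The table built on these criteria reports "The number and percentage of participants meeting PCI for each vital sign (temperature, pulse rate, and pulse oximetry"). On timing and layout, the SAP says that these counts "at Day 28 visit and for any post-baseline visit will be summarized by treatment group in a table". The section mentions no split by direction, no baseline column, no shift table, and no restriction to infants who were within limits at baseline.

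Two other outputs in the section use the same data:

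- "A summary table with descriptive statistics for actual and CFB values, will be presented by visit and treatment group". Under SAP 10.1 the descriptive statistics include the mean, SD, median, minimum and maximum.
- "A participant listing of vital signs will be presented with actual values and a flag for values meeting PCI criteria".

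Two sections later, pedal edema "will be presented by treatment group for baseline and any post-baseline visit" (SAP 11.6.7), so a neighbouring safety table does display baseline status.

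**The concern.** A temperature above the upper limit and one below the lower limit are different safety observations, and the same holds for pulse rate. Counting them as one event means that readings in the direction of no interest inflate both arms and make an excess in the other direction look smaller in relative terms. An infant who is low at one visit and high at another counts once in the any-post-baseline row.

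Enrollment takes place on the day of hospital discharge after acute illness (Protocol 4.1), so some infants may already be outside a limit before the first dose. Without a baseline column the reader cannot tell these from new findings.

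The table matters somewhat more than usual here. No safety laboratory or ECG data are collected (SAP 11.6.3 and 11.6.4), and this is the only by-arm threshold count of measured vital signs. Day 28 is the only scheduled vital-sign measurement at the end of dosing, since the weekly home visits have none (Protocol Table 2). Protocol 2.2 also notes that "contamination is a potential known risk for this type of product". The link from contamination to temperature and pulse is this review's inference and is not stated in the protocol.

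**Working it through.** **Inputs.** The documents state no PCI rate and plan no test of this table, so there is no figure of theirs to reproduce. The number per arm is 177, the evaluable number in SAP 7.1.3 (198 are randomized). All rates below are assumptions chosen to show the mechanism.

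**Set-up.** Let h0 and h1 be the proportions with a high reading on placebo and Bi-26, and l the proportion with a low reading in both arms. At a single visit such as Day 28 one reading cannot be both, so the pooled proportion is h + l.

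- Difference: (h1 + l) − (h0 + l) = h1 − h0, unchanged by pooling.
- Ratio: (h1 + l)/(h0 + l), which moves towards 1 as l grows.
- Index of dilution: difference/SE, with SE = √{[p0(1−p0) + p1(1−p1)]/177}.

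**Equal low readings in both arms, h0 = 5%, h1 = 10%.**

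| Low readings, both arms | Placebo row | Bi-26 row | Difference | Ratio | Difference/SE |
|---|---|---|---|---|---|
| none (high only) | 5% | 10% | 5 points | 2.00 | 1.79 |
| 5% | 10% | 15% | 5 points | 1.50 | 1.43 |
| 10% | 15% | 20% | 5 points | 1.33 | 1.24 |
| 20% | 25% | 30% | 5 points | 1.20 | 1.06 |
| 40% | 45% | 50% | 5 points | 1.11 | 0.94 |

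First row: SE = √[(0.0475 + 0.0900)/177] = 0.0279, and 0.05/0.0279 = 1.79. Row with 20% low: SE = √[(0.1875 + 0.2100)/177] = 0.0474, and 0.05/0.0474 = 1.06.

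With a larger assumed excess, 5% against 12%, the same formula gives 2.38 for high readings alone, and 1.94, 1.70, 1.46 and 1.36 when 5%, 10%, 20% and 30% low readings are added to both arms.

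**Any post-baseline visit.** Here an infant can be low once and high once but is counted once. If the two were independent, the pooled proportion would be h + l − hl. With l = 20%, placebo is 0.05 + 0.20 − 0.01 = 24% and Bi-26 is 0.10 + 0.20 − 0.02 = 28%. The 5-point difference becomes 4 points and the ratio 28/24 = 1.17.

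**Cancellation.** At one visit the pooled difference is zero only if low readings fall on Bi-26 by as much as high readings rise. For example, high 5% against 10% with low 20% against 15% gives 25% in both arms.

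**Baseline.** Randomization makes the expected proportion outside the limits before dosing the same in both arms. Those who remain outside act like l above. They add a similar amount to each row, which is noise and not bias.

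**The case against.** The strongest case against is that this table is not the main detector of fever or infection. SAP 11.6.1 tabulates treatment-emergent, related and serious events by system organ class, preferred term and arm, with further summaries by treatment and follow-up period. Protocol 10.2.1 allows clinically significant vital signs, including worsening from baseline, to be recorded as adverse events. Events are asked about at every visit, including the home visits, whereas vital signs are scheduled on only three days after baseline. Fever recorded as an event would have its own row by arm. The descriptive table gives minimum and maximum by visit and arm, the change-from-baseline table does use baseline, and the listing shows every value. The wording does not forbid directional rows, and separate IDMC outputs are produced under a charter that is not part of these documents.

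Most of this stands, and it limits the point. A reader might infer that an excess of fever on Bi-26 could go unseen in every by-arm output, or that the missing baseline column biases the comparison. The documents support neither inference, for the reasons above. Nor do they give any reason to expect low readings to fall on Bi-26, which cancellation would need. Protocol 2.2 regards the bacteremia case reports for *B. infantis* products as coincidental and reports none with Bi-26.

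The alternatives are still only partial. Adverse event recording depends on the investigator's judgement and generally leaves out findings attributed to the underlying disease. A maximum describes one infant per arm and not a frequency. Opposite shifts can offset each other in a mean. The listing has one PCI flag with no stated direction and no count by arm.

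**Conclusion.** The point holds as a minor one. As written, the only by-arm threshold count of measured vital signs merges two directions for temperature and pulse rate and omits baseline status. The result is relative dilution: under the assumed 5% against 10% with 20% low readings in both arms, the ratio at a single visit falls from 2.0 to 1.2 while the 5-point excess remains visible. The size depends wholly on assumed rates. No test is planned, so difference/SE serves only to index the dilution. Complete cancellation is an arithmetical possibility that needs opposite movements in the two directions. The missing baseline makes the counts harder to interpret but does not bias the arm comparison. SpO2 is not affected by pooling. No efficacy conclusion changes.

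**What to change.** In SAP 11.6.5, specify for temperature and for pulse rate two separate rows, one below the lower limit and one above the upper limit, at baseline, Day 28 and any post-baseline visit. Add, for each direction, a count of participants newly outside that limit, with those within it at baseline as the denominator. Keep the Table 5 limits as they are.

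The cost is a short change of SAP wording, ideally before unblinding, and a few more table rows. No new data are needed. The drawback is smaller counts per row.

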11.6.6 Anthropometrics

Anthropometrics will be assessed and recorded at all clinic visits (Days 1, 28, 56, and 90). Anthropometric measurements will include MUAC (cm), WAZ, WLZ, head circumference (cm), and skinfold thickness (mm). Details on WAZ can be found in Section 11.5.1. Head circumference and MUAC will be measured twice. The average of these measurements will be used for analysis. Skinfold thickness is measured at two locations: the subscapular and triceps. Both measurements will be presented in the outputs.

The WLZ score is calculated similarly to WAZ. Given the weight (kg), sex and length (cm) of a participant, WLZ is calculated as

$$WLZ = \frac{\left(\left(\frac{Weight(kg)}{M}\right)^{L} - 1\right)}{L \times S}$$

Where L, M, and S are pre-determined parameters describe above. The lookup tables for the values of L, M, and S can be found on the WHO website [2]. The average length of the available values from the two independent measurements will be used to derive WLZ at a specific visit. The minimum length of an infant for which a WLZ score can be calculated is 45 cm.

For lengths \geq 45 cm, WLZ will be derived using the above formula and the relevant lookup table. For lengths < 45 cm, parameter estimates for L, M, and S are not available and therefore WLZ will be assumed to be missing.

A summary table with descriptive statistics for actual and CFB values, will be presented by visit and treatment group. A listing with actual and CFB values will be presented. Line graphs with

Confidential Page 40 of 50

the means and 95% CIs for WLZ will be presented by treatment group for visits Baseline, 28, 56, and 90.

11.6.7 Bilateral Pedal Edema

The number and percentage of participants with bilateral pedal edema will be presented by treatment group for baseline and any post-baseline visit.

11.6.8 Physical Examinations

Clinically significant physical examination findings will be provided in a listing.

11.7 Pharmacokinetics/Pharmacodynamics

Pharmacokinetics/pharmacodynamics is not applicable as it is a probiotic study.

11.8 Other Relevant Data Analyses/Summaries

11.8.1 Optional Sub-study: Temperature Logger Data

Temperature logger data will be captured for Days 35 through 49. Values out of range will be indicated as such in the temperature logger data. The number and percentage of participants, with out of normal range temperature readings will be presented by country and treatment group in a summary table for those included in the sub-study in the ITT population. The proportion of participants with the number of days with out-of-range values will be shown for the following categories:

- 0 days
- 1 to 3 days
- 4 to 6 days
- 7 to 9 days
- 10 to 12 days
- ≥ 13 days.

The days when the logger is in transit, ie, the first and last days of temperature logger data, will be excluded from the calculation of the number of days with out-of-range values.

It is expected that 20% of ITT population will be enrolled into the sub-study. A listing will be presented for participants who were included in the sub-study in the ITT population, including daily temperature reading, time of reading and whether the reading was out of normal range.

Confidential Page 41 of 50

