4.5. Optional Sub-study

The aim of this optional, prospective, observational sub-study is to collect information on reliability of refrigeration in the geographic areas where the study is being conducted and where *B. infantis* supplementation may be recommended by WHO if supported by clinical data.

Ensuring universal access to affordable, reliable, sustainable, and modern energy by 2030 is a sustainable development goal. Access to sufficient electricity is essential to reduce poverty as well as improve public services, such as healthcare. While strides have been taken to decrease the number underserved, as of 2020, 733 million people did not have access to electricity in 2020, over 75% (568 million people) of whom lived in sub-Saharan Africa [World Bank 2022]. Per estimates from a year prior, another 1 billion people live with unreliable or insufficient electricity [Sanni 2019].

Electricity deficits are greater in rural areas compared to urban areas [World Bank 2022]. In order to get a geographical cross-representation in this study, each clinical site will be asked to enroll up to 20% of their overall study population into the sub-study.

The selected participants will receive a box containing a temperature data logger to store in the home refrigerator. Participants may refuse enrollment into the sub-study without effecting their participation in the main study.

The box with the temperature data logger will be placed in the refrigerator used by the participant's parent(s)/legal guardian after the participant has completed the study intervention period and during the home visit on Day 35. The box will be collected from the refrigerator at the home visit on Day 49. Participants in the sub-study should keep the box unopened in the refrigerator until the box is collected by the study staff. The study staff will return the box to the clinic so the information from the temperature data logger can be uploaded.

No formal statistical analysis is planned; data will be presented descriptively.

5. Study Population and Eligibility Criteria

A sufficient number of participants will be screened to randomize approximately 396 study participants. Screening will take place while the infant is hospitalized.

Randomization will take place on the day of hospital discharge. Prospective approval of protocol deviations to recruitment and enrollment criteria, also known as protocol waivers or exemptions, is not permitted.

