10.6 Visit Windows/Unscheduled Visits

Data at each visit are to be captured within the following windows for each of the intended visits:

Table 4. Visit windows

Visit name	Visit window	
Screening	≤ 7 days before randomization	
Randomization	Day of hospital discharge, Day 1	
Clinic Visit 1	Day 1	
Home Visits at Week 1	Within ± 1 day of Day 7, ie, Days 6-8	
Home Visit at Week 2	Within ± 1 day of Day 14, ie, Days 13-15	
Home Visit at Week 3	Within ± 1 day of Day 21, ie, Days 20-22	
Clinic Visit 2	Within ± 1 day of Day 28, ie, Days 27-29	
Home Visit at Week 5	Within \pm 2 days of Day 35, ie, Days 33-37	
Home Visit at Week 6	Within \pm 2 days of Day 42, ie, Days 40-44	
Home Visit at Week 7	Within ± 2 days of Day 49, ie, Days 47-51	
Clinic Visit 3	Within ± 2 days of Day 56, ie, Days 54-58	
Clinic Visit 4	Within \pm 2 days of Day 90, ie, Days 88-92	

Additional visit windowing will not be applied. Unscheduled visits will not be included in by-visit summary tables or analysis but may contribute to the Baseline value and listed in by-participant data listings. In the case of a retest (same visit number assigned), the latest available test result as provided in the data transfer for that visit/time point will be used for by-visit summaries.

Confidential Page 24 of 50

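### The refrigerator sub-study bins homes by a raw count of out-of-range days, so homes with equally unreliable refrigerators can be classed differently when visit windows change the logging time

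*SAP*

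**What the plan says.** Protocol 4.5 ties the logger to two home visits. The box is placed "during the home visit on Day 35. The box will be collected from the refrigerator at the home visit on Day 49". SAP 11.8.1 gives the same nominal period: "Temperature logger data will be captured for Days 35 through 49". The protocol synopsis speaks of two weeks of monitoring, and a footnote to the schedule of activities (Protocol Table 2, repeated in SAP Appendix 1) has the box picked up two weeks after placement.

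The two visits have their own windows. SAP Table 4 (section 10.6) allows the placement visit within 2 "days of Day 35, ie, Days 33-37" and the collection visit within 2 "days of Day 49, ie, Days 47-51". The same section says that no further windowing is applied.

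For the analysis, SAP 11.8.1 treats the days in transit as not evaluable: "the first and last days of temperature logger data, will be excluded from the calculation of the number of days with out-of-range values". It then states: "The proportion of participants with the number of days with out-of-range values will be shown for the following categories". The categories are 0, 1 to 3, 4 to 6, 7 to 9, 10 to 12, and 13 or more days. The section also plans the number and percentage of participants with any out-of-range reading, by country and treatment group, and a listing of daily readings. It gives no denominator of evaluable days, no minimum logging time, and no rule for cutting records to a common length.

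**The concern.** A count of bad days has the same meaning for every home only if every home is observed for the same time. The categories fit a record kept exactly on schedule, where the lower limit of the top category is also the maximum attainable. The visit windows allow shorter and longer records. A home with a short record cannot reach the upper categories however poor its refrigerator, and a home with a long record can reach them with some good days.

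The sub-study has one aim, to describe how reliable refrigeration is where the trial is run. A measure that mixes refrigerator performance with visit timing weakens the one result that it exists to give.

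**Working it through.** **Inputs.**
- Placement visit: Day 35, allowed Days 33 to 37 (SAP Table 4).
- Collection visit: Day 49, allowed Days 47 to 51 (SAP Table 4).
- Days dropped: 2, the first and the last (SAP 11.8.1).
- Sub-study size: 20% of the randomized population (SAP 11.8.1), with about 396 randomized (SAP 7.1.3).

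**Formula.** Evaluable days = (collection day − placement day + 1) − 2.

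**The plan's own schedule first.** 49 − 35 = 14 days elapsed, which is the stated two weeks. Evaluable days = 49 − 35 + 1 − 2 = 13, which matches the lower limit of the top category.

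**Within the allowed windows.**

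| Placed | Collected | Evaluable days | Category if out of range every day |
|---|---|---|---|
| Day 37 | Day 47 | 47 − 37 + 1 − 2 = 9 | 7 to 9 |
| Day 35 | Day 48 | 48 − 35 + 1 − 2 = 12 | 10 to 12 |
| Day 35 | Day 49 | 13 | 13 or more |
| Day 33 | Day 51 | 51 − 33 + 1 − 2 = 17 | 13 or more |

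The second row needs no extreme timing: one visit, one day early, moves a refrigerator that failed every day out of the top category.

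**All in-window combinations.** There are 5 × 5 = 25 pairs of placement and collection day:

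| Evaluable days | 9 | 10 | 11 | 12 | 13 | 14 | 15 | 16 | 17 |
|---|---|---|---|---|---|---|---|---|---|
| Pairs | 1 | 2 | 3 | 4 | 5 | 4 | 3 | 2 | 1 |

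In 1 + 2 + 3 + 4 = 10 of the 25 pairs the top category cannot be reached. This counts combinations and does not predict how often each will occur.

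**If data outside Days 35 to 49 were cut.** If only the actual transit days are then dropped, the range is 9 to 15 days. If the first and last retained days are dropped, it is 9 to 13. The top category is out of reach in 12 and 16 of the 25 pairs respectively. Cutting lowers the maximum but does not make logging time constant.

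**Effect on intermediate homes.** A refrigerator out of range on one third of days has an expected count of 9/3 = 3.0 with 9 evaluable days (category 1 to 3), 13/3 = 4.3 with 13, and 17/3 = 5.7 with 17 (both 4 to 6). At the limits, the category 7 to 9 can hold a home out of range on 9 of 9 days (100%) and one out on 7 of 17 (41%).

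**Size of the table.** 0.20 × 396 = 79.2, so about 79 homes.

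**The case against.** The best defence is that the documents describe a fixed period. The SAP names Days 35 to 49, and the protocol speaks of two weeks. If every site collected exactly 14 days after placement, evaluable time would be 14 + 1 − 2 = 13 days for every home and the problem would vanish. This has weight: two early visits or two late visits do leave 13 days, and the 17-day maximum depends on how the text is read. But the two-week wording states the nominal schedule. It does not override the windows given for each visit, and no rule makes collection follow placement by exactly 14 days.

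The extremes are also uncommon combinations. Nine or 17 days requires both visits at opposite limits of their windows, 1 pair in 25 each, while 13 of the 25 pairs give 12 to 14 days. That is why the claim is that homes can be misclassified, not that they generally will be.

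A reader might go further and infer that the table will make some countries look more reliable than others. The documents do not support this. Nothing in them suggests that visit timing differs by country, and early collection shortens the record only if placement is not equally early. The SAP specifies presentation by country for the any-out-of-range summary and does not repeat it for the day-count categories. Nor does the small size of the country groups strengthen the point. With an even split, 79/4 is about 20 homes per country and one home is worth about 5 percentage points, but that would be equally true of a table of percentages.

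Finally, the listing of daily readings would let anyone derive the missing denominator. So no information is lost, but the planned table remains as it is.

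**Conclusion.** The point holds as a minor defect of presentation. The raw day count depends on logging time, which the documents allow to vary: 13 evaluable days on schedule, 9 at the least, and 17 at the most if the two windows are independent and all logger data are kept, or 13 or 15 if data outside Days 35 to 49 are cut. Only exact 14-day spacing between the two visits would remove the problem, and the plan does not require it.

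The consequence is confined to one descriptive table. The sub-study is optional, begins after dosing has ended, and has no formal analysis. No efficacy or safety endpoint is touched.

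**What to change.** In SAP 11.8.1, derive for each home the percentage of evaluable logger days with an out-of-range reading, where evaluable days are the logged days other than the first and last. Summarise this percentage as a continuous variable and in bands set in advance, for example 0%, above 0 to 25%, above 25 to 50%, above 50 to 75%, and above 75%. The cut-points are the team's choice. State whether readings outside Days 35 to 49 are kept.

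Report the number of evaluable days beside the percentages. This matters because the 0% band still depends on logging time: a longer record gives more chance of at least one excursion. Keep the day counts in the listing.

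A ratio would match the SAP's practice elsewhere. Compliance (SAP 11.4) is divided by days on study intervention, and breastmilk feeding (SAP 11.4.2) is a proportion over the days with diary data.

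The cost is a few lines of SAP text and one derived variable. No extra data are needed.
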